#### **5.4. EP547 Dose Rationale**

The 100 mg EP547 dose level to be evaluated in Study EP-547-201 was selected based on a variety of factors to maximize efficacy without adversely impacting safety.

The 100 mg EP547 dose level is well below the highest multiple dose regimen of 225 mg that was preliminarily shown to be safe and well tolerated in healthy subjects from Study EP-547-101. There were no safety or tolerability issues observed in the cholestatic pruritus population in the 75-mg single and 30-mg multiple dose evaluations. Dose selection was further supported by results from PK simulations generated from a custom model that incorporated healthy subject PK, drug-specific metabolism, and anatomical/physiological changes in the liver for patients with Child Pugh A and B. These simulations showed that liver impairment is not expected to alter the PK for a 100 mg dose. PK data in subjects with cholestatic liver disease in Study EP-547-101 are consistent with the simulated predictions and directly demonstrate that PK is similar to that of healthy subjects.

[REDACTED]

The 100 mg EP547 dose is anticipated to be within the therapeutic dosing range of EP547 and therefore should enable demonstration of clinical proof of concept. Although preclinical models to replicate the human phenotype of bile acid and heme metabolite-induced itch are not available for assessment of efficacy, as rodents (and other nonclinical species) do not express the MRGPRX4 receptor, a therapeutic range has been estimated. Such determinations were made using pharmacologic data from 4PB, a small molecule antagonist of MRGPRX4 that relieved intractable itch in patients with PFIC1 (Hasegawa 2014).

[REDACTED]

(AKI) (eg, ‘blood urea increased’ or ‘protein urine present’ adverse events [AEs] as identified by the Standardized Medical Dictionary for Regulatory Activities [MedDRA] Query [SMQ] ‘Acute renal failure’) will be considered AEs of special interest (AESI, [Section 12.1.5](#)). Subjects will be closely monitored for observations of AKI, and study drug may be interrupted for subjects who experience elevations in serum creatinine levels according to the algorithm described in [Section 12.13.4](#).

### **5.5.3. Overall Benefit:Risk Conclusion**

Overall, the safety measures to be employed and the clinical experience to date with EP547 suggest minimal risk to subjects participating in Study EP-547-201. Although a variety of interventions for cholestatic pruritus have been explored, there is currently no medication approved for this indication in adults, and the need for improved treatments remains high. Therefore, development of additional safe and effective, mechanistically based therapeutic options for this condition is essential. If determined to be effective in this study, EP547 may ultimately have the potential to offer substantial relief for patients suffering from cholestatic pruritus, including those enrolled in this study. Considering all available safety information and measures taken to minimize risk to subjects, the overall benefit-risk profile of EP547 is deemed to be acceptable for the conduct of Study EP-547-201.

## **6. TRIAL OBJECTIVES AND PURPOSE**

### **6.1. Primary Objective**

- To assess the efficacy of EP547 compared to placebo on pruritus as assessed by the Worst Itch Numeric Rating Scale (WI-NRS)

### **6.2. Secondary Objectives**

- To assess the efficacy of EP547 compared to placebo on the following:
  - Pruritus-related quality of life using the 5-D Itch Scale
  - Pruritus severity using the Patient Global Impression of Severity (PGI-S)
  - Overall pruritus response to therapy using the Patient Global Impression of Change (PGI-C)
- To assess the safety and tolerability of EP547
- To assess the PK of EP547

### **6.3. Exploratory Objectives**

[figure not shown]
## 7. INVESTIGATIONAL PLAN

### 7.1. Overall Study Design

EP-547-201 is a randomized, double-blind, placebo-controlled study to evaluate the effects of EP547 on pruritus over 6 weeks in subjects with cholestatic pruritus due to PBC or PSC. Where allowed per regulatory/local requirements, subjects will be able to attend study visits at a physical study site as well as remotely (hybrid model) or at a virtual site where all visits will be conducted remotely (decentralized model). For both the hybrid and decentralized models, a home health nurse visit at the subject’s home or work and a telemedicine visit with the study site staff (eg, smartphone or computer) will be arranged to conduct procedures for each remote study visit.

As shown in Figure 1, the study includes a Screening Period of up to 4 weeks to assess subject eligibility; a 6-week Double-Blind Treatment Period; a 6-week Open-Label Extension Period; and a 2-week Safety Follow-Up Period after administration of the last dose of study drug (EP547 or placebo). Approximately 58 subjects will be randomized to receive either 100 mg doses of EP547 or placebo orally (PO) QD in a 1:1 ratio. In the Open-Label Extension Period, all subjects will receive 100 mg doses of EP547.

**Figure 1: EP-547-201 Study Design**

PO = oral, QD = once daily.

a For the decentralized model, enrollment/randomization and the first dose of study drug may be separated by up to 10 additional calendar days to allow for home delivery of study drug. When enrollment/randomization and first dose of study drug are on separate days, the first dose of study drug is considered Day 1.

b Any subject who completes the Open-Label Extension Period or discontinues study drug (EP547 or placebo) early will complete a follow-up visit approximately 2 weeks ( $\pm 3$  days) after the last dose of study drug.

#### 7.1.1. Screening Period

The Screening Period will consist of 1 study visit (Visit 1). During this period, subjects will undergo assessments to determine study eligibility. Visit 1 (Day-28 to Day -1) may be conducted over more than 1 day but must be completed between Day -28 and Day -1.

### **7.1.2. Double-Blind Treatment Period**

The Double-Blind Treatment Period will consist of 5 study visits (Visits 2, 3, 4, 5, and 6 [Day 1 and Weeks 1, 2, 3, and 6]). During this period, all subjects who meet eligibility requirements will be enrolled into the study and randomized to receive double-blind, PO, QD doses of EP547 or placebo for 6 weeks beginning on Visit 2 (Day 1). Subjects will be randomized to receive either 100 mg doses of EP547 or placebo in a 1:1 ratio. Randomization will be conducted centrally via an Interactive Web Response System (IWRS) and stratified based on type of cholestatic disease (PBC, PSC). Visit 2 (Day 1) will not have a visit window; however, for the decentralized model, enrollment/randomization and the first dose of study drug may be separated by up to 10 additional calendar days to allow for home delivery of study drug. When enrollment/randomization and first dose of study drug are on separate days, the first dose of study drug is considered Day 1. All other visits in the Double-Blind Treatment Period will have a visit window of  $\pm 3$  days.

### **7.1.3. Open-Label Extension Period**

The Open-Label Extension Period will consist of 2 study visits (Visit 7 [Week 9] and Visit 8 [Week 12]). During this period, all subjects who complete the Double-Blind Treatment Period and are still receiving study drug will receive open-label 100 mg doses of EP547. Visit 7 and Visit 8 will have a visit window of  $\pm 3$  days.

### **7.1.4. Safety Follow-Up Period**

Any subject who completes the Open-Label Extension Period or discontinues study drug (EP547 or placebo) early will complete a follow-up visit (Visit 9) approximately 2 weeks ( $\pm 3$  days) after the last dose of study drug.

## **7.2. End of Study**

A subject is considered to have completed the study if he/she has completed all phases of the study, including the last study visit (ie, the Follow-Up Visit [Visit 9]).

The end of the study is defined as the date of the last study visit of the last subject in the study globally.

## **7.3. Number of Subjects**

Approximately 58 subjects with cholestatic pruritus due to PBC or PSC will be randomized in the study.

## **7.4. Dose Adjustment Criteria**

Dosages for study drug should be maintained constant during the study. However, dosing of study drug may be interrupted or discontinued due to safety findings. Refer to [Section 8.5](#) for guidance on mandatory discontinuation of study drug due to severe and related AEs.

## **7.5. Criteria for Study Termination**

The Sponsor may terminate the study at a study site at any time (eg, Good Clinical Practice [GCP] noncompliance or poor study data quality). If instructed by the Sponsor or designee, the

Investigator must implement the termination in a timeframe to ensure subject safety and well-being. Refer to [Section 8.5.2 \(Discontinuation from the Study\)](#) for instructions for subjects whose participation from the study is discontinued.

The Investigator and/or Sponsor (or designee) must notify the Institutional Review Board/Independent Ethics Committee (IRB/IEC) of discontinuation of a site or the study and the reason for doing so.

## **8. SELECTION AND WITHDRAWAL OF SUBJECTS**

Subjects who have an exclusionary result at Visit 1 may have that assessment repeated once at the discretion of the Investigator within the screening window and be enrolled if a repeat assessment is within the indicated range as specified below for participating in the study.

### **8.1. Subject Inclusion Criteria**

To be eligible for study participation, all subjects must meet all the following inclusion criteria:

1. Age 18 to 80 years, inclusive
2. Has experienced self-reported daily or near-daily moderate to severe pruritus before Screening
3. Has a mean daily WI-NRS score indicative of moderate to severe pruritus (score  $\geq 4$ ) during Screening (Day -7 through Day -1); data from at least 4 of the 7 days are required to be considered an acceptable profile
4. If currently taking medications to treat the cholestatic disorder (including obeticholic acid [OCA]), must be on a stable dose for >12 weeks before Screening and plans to maintain the regimen throughout the study
5. If currently taking a fibrate, must be on a stable dose for >12 weeks before Screening and plans to maintain the regimen throughout the study
6. Either is not treated with or has been on a stable regimen with any medications to treat pruritus for >4 weeks before Screening and plans to maintain the regimen throughout the study
7. If female, must have a negative serum pregnancy test at Screening and be willing to not donate eggs from Screening until after the last dose of study drug and:
  - a. Is surgically sterile; or
  - b. Has been amenorrhoeic for  $\geq 1$  year without an alternative medical cause; or
  - c. If of childbearing potential, must agree to use at least 1 form of an acceptable method of contraception from Screening until the last dose of study drug. Acceptable birth control methods include:

---

 Women of childbearing potential are defined as those who are fertile, following menarche and until becoming postmenopausal unless permanently sterile. Permanent sterilization methods include hysterectomy, bilateral salpingectomy, and bilateral oophorectomy. A postmenopausal state is defined as no menses for 12 months without an alternative medical cause.

- Barrier methods of contraception (eg, male condom, female condom, cervical cap or diaphragm, and contraceptive sponge)
  - Combined (estrogen and progestogen containing) hormonal contraception associated with inhibition of ovulation
  - Progestogen only hormonal contraception
  - Intrauterine device
  - Intrauterine hormone releasing system
  - Bilateral tubal occlusion
  - Vasectomized partner
  - Sexual abstinence (complete sexual abstinence defined as refraining from heterosexual intercourse for the entire period of risk associated with study drug), the reliability of which needs to be evaluated in relation to the duration of the clinical study and the preferred and usual lifestyle of the subject
8. Must be able to communicate well with the Investigator, understand and comply with the requirements of the study, and understand and provide written consent
9. For subjects with concomitant inflammatory bowel disease (IBD):
- a. Colonoscopy (if subject has a colon) or other appropriate endoscopic procedure within 18 months of Day 1 confirming no dysplasia or colorectal cancer
  - b. Subjects with Crohn's disease (CD) must be in remission as defined by a Crohn's Disease Activity Index (CDAI) <150 at Screening
  - c. Subjects with ulcerative colitis (UC) must have a Partial Mayo Scoring Index score  $\leq 3$  with no individual sub-score exceeding 1 point at Screening

Subjects with PBC must also meet the following inclusion criteria to be eligible for study participation:

10. Documented history of PBC that is consistent with the American Association for the Study of Liver Diseases (AASLD) Practice Guidelines ([Lindor 2019](#)), defined as having  $\geq 2$  of the following 3 factors upon diagnosis:
- a. History of elevated alkaline phosphatase (ALP) levels
  - b. Historic positive antimitochondrial antibody (AMA) or AMA-M2 by immunofluorescence, enzyme linked immunosorbent assay (ELISA), or immunoblot or if AMA is negative, positive for PBC-specific antibodies (anti-GP210 and/or anti-SP100)
  - c. Liver histology at any point in time consistent with PBC
11. If currently taking ursodeoxycholic acid (UDCA), must be on a stable dose of not more than 20 mg/kg/day for  $\geq 12$  weeks. If not currently taking UDCA, must not be treated with UDCA within 12 weeks before Screening or plan to be treated with UDCA during the study

Subjects with PSC must also meet all the following inclusion criteria to be eligible for study participation:

12. Documented history of PSC based on either cholangiography (ie, magnetic resonance cholangiopancreatography, endoscopic retrograde cholangiopancreatography, or percutaneous transhepatic cholangiogram) or if small duct PSC, confirmed by typical histologic evidence of PSC for  $\geq 1$  year (EASL 2009, Chapman 2010)
13. If currently taking UDCA, must be on a stable dose of not more than 23 mg/kg/day for  $\geq 12$  weeks. If not currently taking UDCA, must not be treated with UDCA within 12 weeks before Screening or plan to be treated with UDCA during the study

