### 9.4.1. Screening Period

#### 9.4.1.1. Visit 1 (Day -28 to Day -1)

During the Screening Period, subjects will undergo assessments to determine their study eligibility. Subjects will be screened and should meet all inclusion criteria and none of the exclusion criteria to be enrolled in the study. Any questions regarding eligibility may be discussed with the Medical Monitor.

The following assessments may be conducted over more than 1 day but must be completed between Day -28 and Day -1:

- Completion of informed consent before performance of any study procedures or assessments
- Medical history
- Height
- Assessment of baseline concomitant medications, including:
  - All medications taken within 14 days before Screening
  - Medications taken to treat a cholestatic disorder within 12 weeks before Screening

- Medications known to impact pruritus within 4 weeks before Screening
- Assessment of AEs
- Partial Mayo Score (for subjects with UC only)
- CDAI (for subjects with CD only)
- Physical examination
- Vital signs
- Standard 12-lead ECG
- Transient elastography (TE; FibroScan; if an eligible historical TE is not available within 6 months of Screening)
- Laboratory assessments:
  - Urinalysis
  - HIV, hepatitis A virus (HAV), hepatitis B virus (HBV), hepatitis C virus (HCV), and hepatitis E virus (HEV) serology
  - Serum pregnancy test (females only)
  - Chemistry and hematology
  - Coagulation
  - IgG4
- Eligibility check
- Receive questionnaire training (to be conducted before completing the daily WI-NRS for Day -14)

Subjects will be instructed to complete the WI-NRS daily, in the morning, and at the same time of day, beginning at Day -14 to the Safety Follow-Up Visit. For days that coincide with a study visit (for Visit 2 and beyond), the WI-NRS is to be completed before the study visit.

Screening results will be reviewed by the Investigator to determine the subject's eligibility. Subjects who are confirmed to be eligible will be asked to return to the site for Visit 2 (Day 1) for enrollment and randomization.

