#### **9.4.2. Double-Blind Treatment Period**

##### **9.4.2.1. Visit 2 (Day 1)**

Subjects who continue to meet study eligibility requirements will be enrolled and randomized during Visit 2 (Day 1).

Subjects will undergo the following procedures at Visit 2 (Day 1):

- Confirm that the WI-NRS has been completed daily from Day -14 to the morning prior to this visit

- Questionnaires:
  - 5-D Itch Scale
  - PGI-S

- Assessment of concomitant medication usage
- Assessment of AEs
- Vital signs
- Standard 12-lead ECG
- Laboratory assessments:
  - Urine pregnancy test (females only)
  - Urinalysis
  - Kidney-related biomarkers (blood and urine)
  - Chemistry and hematology
  - Coagulation
  - Bile acids and heme metabolites
  - Retained samples for future analysis (blood and urine)
  - Genotyping (optional)
  - Thyroid hormones: thyroid-stimulating hormone (TSH) and free thyroxine (T4)
- Blood sample draw for PK assessment predose and  postdose
- Eligibility check
- Randomization to 100 mg EP457 or placebo in a 1:1 ratio via IWRS
- Dispense double-blind study drug

For the decentralized model, enrollment/randomization and the first dose of study drug may be separated by up to 10 additional calendar days to allow for home delivery of study drug. If enrollment/randomization is conducted on a separate day than dosing, the eligibility check should also be conducted during the same day as enrollment/randomization. Additionally, confirmation that WI-NRS has been completed daily and assessments of concomitant medication usage and AEs are to be conducted on both days (ie, date of enrollment/randomization and date of first dose). All other assessments listed above are to be conducted on the date of first dose only.

Upon completion of the assessments listed above, double-blind study drug is to be administered orally as intact tablets (swallowed whole, not chewed or crushed), and taken with water.

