#### **11.1.1. Worst Itch Numeric Rating Scale (WI-NRS)**

Subjects will be asked to rate the severity of their worst level of itching in the past 24 hours in the morning, and at the same time of day, using the WI-NRS. The WI-NRS is an 11-point scale ranging from 0 (No Itching) to 10 (Worst Itching Imaginable) ([Phan 2012](#)) and requires approximately 1 minute to complete. Higher scores indicate greater itch severity. Itching severity scores collected via the WI-NRS have been categorized in the literature as mild (<4), moderate ( $\geq 4$  to <7), or severe ( $\geq 7$ ) ([Fishbane 2020](#), [Hirschfield 2020](#), [Levy 2020](#), [Stander 2020](#)). An example of the WI-NRS is included in [Appendix B](#).

Subjects will be instructed to complete the WI-NRS daily, in the morning, and at the same time of day, beginning at Day -14 to the Follow-Up Visit. For days that coincide with a study visit (for Visit 2 and beyond), the WI-NRS is to be completed before the visit.

The WI-NRS scores from Day -7 through Day -1 will be averaged together to confirm compliance and determine subject eligibility for continued participation regarding pruritus sensation. The average WI-NRS score using the daily values from the week before the first dose of study drug (Visit 2 [Day 1]) will serve as the baseline score. The 7 daily WI-NRS scores prior to Visit 6 (Week 6) will be averaged together for primary endpoint analyses. Data from at least 4 of the 7 days for each week are required to be considered an acceptable profile.

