## **16. STUDY MANAGEMENT**

### **16.1. Protocol Deviations**

The Investigator is not permitted to deviate from the protocol in any major way without proper notification to the Sponsor (or designee). Only the Sponsor may revise the protocol. Any change in study conduct considered necessary by the Investigator will be made only after consultation with the Sponsor, who will then issue a formal protocol revision to implement the change and obtain regulatory approval. The only exception is when the Investigator considers a subject's safety to be compromised if immediate action is not taken.

In the event of an important deviation from the protocol, the Investigator or designee must contact the Sponsor or representative at the earliest possible time. This will allow an early joint decision regarding the subject's continuation in the study.

Examples of important protocol deviations include the following:

- Subject did not give appropriate informed consent
- Inclusion or exclusion criteria not satisfied
- Non-permitted concomitant medications that may meaningfully impact efficacy or safety outcomes
- Meaningful dosing error
- Randomization error

The Investigator and Sponsor will both document this decision. The IRB/IEC will be informed of all important protocol deviations by the Investigator in accordance with established procedures.

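### Can the WI-NRS entry criterion be applied when a decentralized subject is randomised up to 10 days before the first dose?

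*Protocol*

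**What the plan says.** Criterion 3 in Protocol 8.1 (repeated in the Synopsis) asks for a mean WI-NRS of at least 4 "during Screening (Day -7 through Day -1); data from at least 4 of the 7 days are required to be considered an acceptable profile". Section 11.1.1 uses the same seven days: the scores are "averaged together to confirm compliance and determine subject eligibility for continued participation regarding pruritus sensation".

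Section 7.1.2 lets first dose follow randomisation by up to 10 calendar days in the decentralized model, for home delivery, and sets the day count: "When enrollment/randomization and first dose of study drug are on separate days, the first dose of study drug is considered Day 1".

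On timing, Section 9.4.1.1 says "Subjects will be screened and should meet all inclusion criteria and none of the exclusion criteria to be enrolled in the study". It then has the investigator review the screening results and bring back those found eligible for Visit 2, where they are randomised. Section 9.4.2.1 lists an eligibility check at Visit 2 and adds that, if the dates differ, "the eligibility check should also be conducted during the same day as enrollment/randomization". Diary completion is confirmed on both dates, and study drug is taken only after the visit's assessments are finished.

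Two further places matter. Protocol 14.2 describes the target population as having a mean WI-NRS of at least 4 at baseline. SAP 4.1.2 fixes that baseline as Day -6 through Day 1, counted from first dose.

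**The concern.** Read strictly, these rules do not fit together. Study days are numbered from first dose, so Day -7 to Day -1 is the week before dosing. Eligibility, however, is to be settled before randomisation. With a long delivery gap, most or all of that week lies in the future when the subject is randomised. Amendment 2.0 introduced the split dates and re-anchored the analysis baseline for them, but left this window alone.

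Three things could follow:

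- Sites might judge similar subjects on different weeks.
- A subject found below 4 after randomisation but before dosing would drop out of the Full Analysis Set, which requires at least one dose (Protocol 14.1).
- A subject dosed despite failing would stay in the Full Analysis Set but be an important deviation under Section 16.1 ("Inclusion or exclusion criteria not satisfied") and leave the Per Protocol Set (SAP 4.2).

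With 29 planned per arm and 26 completers wanted, the allowance is 29 − 26 = 3 per arm, so avoidable losses would be unwelcome.

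**Working it through.** **Inputs.** Window Day -7 to Day -1, minimum 4 of 7 scores (Protocol 8.1). Day 1 = first dose, gap g up to 10 days (Protocol 7.1.2). No Day 0 (SAP 4.1.5). Diary starts at Day -14 (Protocol 11.1.1). Baseline Day -6 to Day 1 (SAP 4.1.2). The documents state no figure for days available at randomisation, so there is none to reproduce.

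**Reading A: window counted from first dose.** Let R be the randomisation date, so first dose is R + g and Day -k is R + g − k. The window runs from R + g − 7 to R + g − 1. Days in it up to and including R number max(0, 8 − g) for g of 1 or more. Leaving out the score on the morning of R gives max(0, 7 − g). At g = 0 the window is R − 7 to R − 1, the full seven days.

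| Gap g (days) | Scores possible at randomisation | Without that morning's score |
|---|---|---|
| 1 | 7 | 6 |
| 2 | 6 | 5 |
| 3 | 5 | 4 |
| 4 | 4 | 3 |
| 5 | 3 | 2 |
| 6 | 2 | 1 |
| 7 | 1 | 0 |
| 8 to 10 | 0 | 0 |

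The minimum of four is out of reach at gaps of 5 to 10 days (4 to 10 on the stricter count). By the morning of dosing, all seven days have passed at every gap.

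**Reading B: window is the week before randomisation.** Here the window is R − 6 to R, or R − 7 to R − 1 without that morning's score. All of it is past at randomisation. The only limit is the diary. If Day -14 is counted from first dose, the diary starts at R + g − 14. Days covered are 7 (7) up to gap 7, then 7 (6) at gap 8, 6 (5) at gap 9 and 5 (4) at gap 10. Four scores are possible at every permitted gap.

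**Distance from baseline.** Under reading A, the eligibility window and the SAP baseline share Day -6 to Day -1, which is 6 of 7 days. Under reading B, the pre-randomisation week is Day -(g+6) to Day -g, or Day -(g+7) to Day -(g+1). Its overlap with Day -6 to Day 1 is max(0, 7 − g), or max(0, 6 − g). At a 5-day gap that is 2 (1) days, and from gap 7 (6) upward it is zero.

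**Which reading does the text support?** For B: the criterion says the window falls in Screening; randomisation sits in the Double-Blind Treatment Period (Section 7.1.2); Section 9.4.1.1 has eligibility confirmed before the subject returns to be randomised; and the gap is described as additional days. For A: the Day 1 rule itself, and the labelling of Screening as Day -28 to Day -1. If A is meant, the word *also* in Section 9.4.2.1 makes the randomisation-day check an extra one beside the Visit 2 check, and Section 11.1.1 speaks of continued participation. Both fit a check completed on the dosing day.

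**The case for a change.** The best case for a change is that the parenthesis in criterion 3 gives numbered days, the protocol numbers days from first dose, and nowhere is randomisation named as the anchor. The two candidate weeks share no days at gaps of 8 to 10 (7 to 10 on the stricter count). The dosing-day check on reading A comes after randomisation, and Section 9.4.2.1 spells out diary completion, not a re-test of the mean. A sentence or two would settle it.

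It stands that the text does not name the anchor. The rest carries less weight. On reading A a failure is found before any drug is taken and without knowledge of the assignment. It goes to the process in Section 16.1, where the sponsor is contacted and "This will allow an early joint decision regarding the subject's continuation in the study". Eligibility questions may also go to the Medical Monitor (Section 9.4.1.1).

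Nor is the obvious amendment free. Fixing the window to the week before randomisation, with baseline left at first dose, could admit subjects whose baseline is below 4. They would not match the population in Protocol 14.2, and they would fall into the SAP 4.4.7.8 subgroup labelled moderate (below 7). A full pre-randomisation week at a 10-day gap would also need the diary to start at Day -16 (Day -17), 2 (3) days earlier than now.

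**Conclusion.** This is a gap in wording that sites can fill sensibly, and no change to the plan follows. On the reading that Screening ends at randomisation, the criterion can be applied on time at every permitted gap. On the reading that counts from first dose, it cannot be verified at randomisation for gaps of 5 to 10 days (4 to 10), but it can be verified before dosing, and the window then nearly coincides with the analysis baseline (6 of 7 days). Each reading has a cost: an occasional exclusion after randomisation on one, some drift between entry score and baseline on the other. Choosing between them is a fair trade-off.

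The primary analysis is not biased on either reading, because the scores are pre-dose and blinded and the baseline is tied to first dose. What remains is a possible small loss of subjects from the Full Analysis Set or the Per Protocol Set, confined to decentralized subjects with split dates. The documents give neither their number nor the usual gap, so that loss cannot be sized. The conclusion assumes that the criterion is judged before dosing and without knowledge of the assignment. The study manuals on remote visits, which may settle the anchor, were not available.
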